- ^z The reporting of AEs will begin at Induction Day 1 post first dose for all randomized patients. The reporting of SAEs for any patient will begin from the time written informed consent/assent is signed through the last visit. Any SAE that is ongoing when the patient completes the trial or discontinues from the trial will be followed by the Investigator until the event has resolved, stabilized, or returned to Baseline status.

Abbreviations: β -hCG = beta human chorionic gonadotrophin; DLCO = diffusion capacity of the lung for carbon monoxide; Early Term = Early Termination; ECG = electrocardiogram; EoT = End of Treatment; I = Induction Period; Igs = immunoglobulins; M = Maintenance Period; PD = pharmacodynamic; PK = pharmacokinetic; [REDACTED]; TB = tuberculosis

Table 2: Cardiac Monitoring During Dose Escalation

Procedure ^a	Induction Day 1		
	Predose	Hours 1, 2, 3, 4, 5	Hour 6
Vital signs ^b	X	X	X
12-lead ECG	X ^c		X
Assess Discharge Criteria ^d			X

^a These assessments should also be conducted as on Induction Day 1 at the indicated times on Days 5 and 8 if issues are identified on the day prior to dose escalation.

^b Resting pulse and blood pressure in the sitting position at each time point.

^c Baseline or predose ECG should be provided by the site and be available for comparison to the postdose ECG in order to determine if discharge criteria are met.

^d See [Section 12.1.10](#) for discharge criteria and monitoring guidelines. Additional observation should be instituted until the finding has resolved in the following situations: pulse (per hourly vital signs measurement) 6 hours postdose is < 45 bpm; pulse (per hourly vital signs measurement) 6 hours postdose is at the lowest value postdose and lower than any other timepoint (unless this value is greater than or equal to baseline); ECG 6 hours postdose shows new onset second degree or higher AV block; for adult patients, the ECG 6 hours postdose shows a prolonged QTcF interval (> 450 msec males, > 470 msec females); for adolescent patients (> 450 msec for both males and females)

Abbreviations: AV = atrioventricular; ECG = electrocardiogram; QTcF = Fridericia's corrected QT interval.

[REDACTED]

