12.1.4. Electrocardiogram

The 12-lead digital ECG devices will be provided to each clinical site by the central ECG laboratory for the duration of the trial. Detailed instructions describing the process for recording and transmission of the digital ECGs will be outlined in the trial-specific manual and provided to the site before the start of the trial. Paper versions of ECG tracings recorded at the times specified in the Schedule of Events ([Section 7.1](#)) will be printed and photocopied to preserve the ink if necessary, and kept at the site as source documentation.

An ECG will be performed while resting. The screening ECG report from the central reader must be available to confirm patient eligibility before randomization. Electrocardiograms will be performed before and 6 hours after the first dose of investigational drug administration for all patients on Induction Day 1 while the patient is in the clinic. The 6 hour postdose ECG will be evaluated by the treating physician, with input if needed from a local cardiologist or a central reader to confirm if extended monitoring is required. Additional ECG monitoring will be performed on Days 5 and 8 if cardiac issues are identified on the prior day of dose escalation, as described in [Section 12.1.10](#).

Only clinically significant abnormalities should be reported in the medical history/current medical conditions or the AE eCRF. Clinically significant findings must be discussed with the Medical Monitor before enrolling the patient in the trial.

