If any of the following criteria are met, additional extended monitoring should be instituted until the finding has resolved. Baseline and hourly vital signs measurements (Hours 1 through 6) should be used to assess pulse (criteria 1 and 2 below) and ECG device results should only be used to assess for AV block and QTcF interval (criteria 3 and 4 below).

1. The pulse 6 hours postdose is < 45 bpm
2. The pulse 6 hours postdose is at the lowest value postdose and lower than any other timepoint (suggesting that the maximum PD effect on the heart may not yet have occurred), unless this value is greater than or equal to baseline
3. The ECG 6 hours postdose shows new onset second degree or higher AV block
4. For Adult patients, the ECG 6 hours postdose shows a prolonged QTcF interval (> 450 msec for males, > 470 msec for females)

Should postdose symptomatic bradycardia occur, the treating physician should be notified and he or she should initiate appropriate management, begin continuous ECG monitoring, and continue observation until the symptoms have resolved.

Should a patient require pharmacologic intervention for symptomatic bradycardia, continuous overnight ECG monitoring in a medical facility should be instituted, and the first dose monitoring strategy should be repeated the following day (Day 2). The first dose monitoring strategy should also be repeated at Day 5 or at Day 8 if any cardiac safety issues were observed on the previous Day of dose escalation (see [Table 2](#)).

Patients should have written instruction on when to return to the clinic and a 24-hour contact phone number to call in the event of any new or warranted symptoms (eg, chest pain, dizziness, palpitations, syncope, nausea, vomiting). Patients should be instructed not to drive on the same day after the first dose of investigational drug administration.

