11.5. Vital Sign Measurements

Systolic and diastolic blood pressure (SBP and DBP) and pulse (HR) will be assessed in a sitting position and collected at each visit. On Day 1 of treatment for the IP, careful cardiac monitoring of the patients is required. Resting pulse and blood pressure in the sitting position will be measured before the first dose of investigational drug and every hour for at least 6 hours thereafter. For the hourly measurements after investigational drug administration, HR and sitting blood pressure will be measured once and recorded in the eCRF. The first dose monitoring strategy should also be repeated at Day 5 or at Day 8 if any cardiac safety issues were observed on the previous Day of dose escalation.

Summary statistics of actual values and changes from Baseline in vital signs will be provided by visit (Baseline, Week 5, Week 10, highest value post-baseline during IP, lowest value post-baseline during IP, last available measurement while on treatment during IP). On Day 1, hourly

changes from predose up to hour 6 in blood pressures and HRs will be summarized for all patients.

Patient's lowest heart rate during 6-hour cardiac monitoring on Day 1 will be summarized by number and percentage by category: ≥ 65 , 60-64, 55-59, 50-54, 45-49, 40-44, 35-39, < 35 bpm, as well as < 40 bpm and < 45 bpm.

The number and percentage of patients requiring extended cardiac monitoring beyond hour 6 on Day 1 or requiring monitoring on Study Days 5 and/or 8 will be summarized by Day: Day 1, Day 5, and Day 8. A listing of these patients will be presented that shows the hourly change from the pre-dose assessment at each of the available Baseline, Study Day 5, and Study Day 8 visits by patient for HR and blood pressures.

The number and percentage of patients with clinically relevant abnormalities defined below will be summarized overall and by visit (Week 5, Week 10, last available while on treatment during IP) and overall. The denominator will be the number of patients with observed data at both Baseline and respective post-Baseline visit, unless specified otherwise.

- SBP:
 - > 140 mmHg post-Baseline
 - > 160 mmHg post-Baseline
 - > 180 mmHg post-Baseline or an increase from baseline of > 40 mmHg
 - > 180 mmHg post-Baseline (denominator will be the number of patients with Baseline SBP ≤ 180)
 - an increase from Baseline of > 40 mmHg
 - < 90 mmHg post-Baseline or a decrease from Baseline of > 30 mmHg
 - < 90 mmHg post-Baseline

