 - < 90 mmHg post-Baseline (denominator will be the number of patients with Baseline SBP ≥ 90)
 - a decrease from Baseline of > 30 mmHg
- DBP:
 - > 90 mmHg post-Baseline
 - > 100 mmHg post-Baseline
 - > 105 mmHg post-Baseline or an increase from Baseline of > 30 mmHg

- >105 mmHg post-Baseline (denominator will be the number of patients with Baseline DBP \leq 105)
- an increase from Baseline of > 30 mmHg
- <50 mmHg post-Baseline or a decrease from Baseline of > 30 mmHg
 - <50 mmHg post-Baseline
 - <50 mmHg post-Baseline (denominator will be the number of patients with Baseline SBP \geq 50)
 - a decrease from baseline of > 30 mmHg
- HR:
 - >100 bpm post-Baseline
 - >120 bpm post-Baseline or an increase from baseline of > 20 bpm
 - >120 bpm post-Baseline (denominator will be the number of patients with Baseline HR \leq 120)
 - an increase from Baseline of > 20 bpm
 - <60 bpm post-Baseline
 - <45 bpm post-Baseline or a decrease from Baseline of > 20 bpm
 - <45 bpm post-Baseline (denominator will be the number of patients with Baseline HR \geq 45)
 - a decrease from Baseline of > 20 bpm

The number and percentage of patients with clinically relevant abnormalities during cardiac monitoring, including those beyond hour 6 on Day 1, will be summarized overall and by hour during pre-defined 6-hour monitoring window on Day 1, as well as overall during cardiac monitoring (Days 1/5/8). The denominator will be the number of patients with observed data at both Baseline and respective post-Baseline timepoint.

Discharge Status eCRF data after receiving extended cardiac monitoring after 6 hours will be summarized by number and percentage of patients. All data reported on the Discharge Status eCRF will be listed, including the reason for extended monitoring.

Box plots will be provided to display the distribution of vital signs results by timepoint on Day 1 up to hour 6, or by visit. In addition, line plots of means and SEs will be created to display the

actual values and change from pre-dose by timepoint on Day 1 up to hour 6. Line plots of means and SEs will also be created to display the actual values and change from Baseline by visit.

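### Table 2 footnote a ties the Day 5 and Day 8 repeat of cardiac monitoring to days with no scheduled assessment, and differs from the other four statements of the rule

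*Protocol*

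**What the plan says.** The rule appears in five places, in three wordings.

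- **Protocol Table 2, footnote a (Section 7.1):** the Induction Day 1 assessments are repeated "on Days 5 and 8 if issues are identified on the day prior to dose escalation".
- **Protocol 12.1.4:** "Additional ECG monitoring will be performed on Days 5 and 8 if cardiac issues are identified on the prior day of dose escalation". The sentence then refers to 12.1.10. SAP 11.8 states the same rule in the same words.
- **Protocol 12.1.10:** the first-dose monitoring is to be "repeated at Day 5 or at Day 8 if any cardiac safety issues were observed on the previous Day of dose escalation". The sentence ends by citing Table 2. SAP 11.5 repeats the condition: "if any cardiac safety issues were observed on the previous Day of dose escalation".

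Protocol 9.1.1 gives 0.25 mg on Days 1 to 4, 0.5 mg on Days 5 to 7 and 1 mg from Day 8. Under 12.1.10 full monitoring is required on Day 1. If a patient meets a listed criterion at Hour 6, "additional extended monitoring should be instituted until the finding has resolved". Footnote d of Table 2 sends the reader to 12.1.10 for the discharge criteria and monitoring guidelines.

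**The concern.** This is an operative safety instruction at two dose increases, and its condition is worded in ways that can point to different days. Footnote a also points to days on which no one is scheduled to examine the patient.

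The difference matters when a finding appears on Day 1 and has gone by Day 4. The protocol's own procedure makes that likely, because a Day 1 finding is watched until it resolves. On the natural reading of 12.1.10 such a patient is monitored again at the Day 5 dose. On the literal reading of footnote a the patient is not. If the repeat is missed, the next scheduled vital signs are at Week 5 and the next scheduled 12-lead ECG is at Week 10 (Table 1).

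**Working it through.** The plan states no figure to reproduce. The check compares the wordings with the dose steps and the schedule.

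**Inputs.** Dose increases on Day 5 and Day 8 (protocol 9.1.1, 9.3). Scheduled visits: Day 1, then Visit I 2 at Day 35±5, which is Days 30 to 40 (Table 1).

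**Reference days.**

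| Step | Footnote a, literal | 12.1.4, 12.1.10, SAP 11.5, 11.8, natural reading | Difference |
|---|---|---|---|
| Day 5 | 5 − 1 = Day 4 | Day 1 (previous escalation day) | 4 − 1 = 3 days |
| Day 8 | 8 − 1 = Day 7 | Day 5 (previous escalation day) | 7 − 5 = 2 days |

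The two readings share no reference day.

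**Is anything assessed on those days?** Nothing is scheduled on Day 4 or Day 7. Day 1 is always monitored. Day 5 is monitored only if its own trigger was met. So even on the natural reading, the Day 8 trigger rests on a formal assessment only in patients already re-monitored on Day 5.

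**Do the cross-references decide it?** No. Section 12.1.4 sends the reader to 12.1.10, 12.1.10 cites Table 2 for this rule, and Table 2 footnote d cites 12.1.10. The visible text does not say which prevails.

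**Is the natural reading the only one?** No. Protocol 9.1.1, 9.1.3 and 9.3 also use dose escalation for the whole first week. On that usage, the prior day of dose escalation could mean the immediately preceding day, Day 4 or Day 7. All five statements would then agree, but on unassessed days. Under either reading the days need to be named.

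**Illustration.** Take an adult man whose Day 1 record shows that "the ECG 6 hours postdose shows a prolonged QTcF interval" (above 450 msec), without symptoms, and who is observed until it resolves. The Day 2 repeat in 12.1.10 does not reach him, because it follows drug treatment for symptomatic bradycardia. Appendix 3 mentions discontinuation for clinically important bradycardia or AV conduction block and does not name QTcF. He can therefore reach the Day 5 dose. If his finding counts as a cardiac safety issue, a term the visible text does not define, 12.1.10 on its natural reading repeats the monitoring and footnote a taken literally does not.

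**The case against.** The strongest reply is that there is no true conflict. The four other statements can be read to match footnote a, and the mutual citations show that one rule was intended. A site that reads both places would probably act on the Day 1 finding. That lowers the chance of an omission. It does not remove the defect, because no sentence names the day.

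A second reply is that harm is limited, and this stands. Under Section 12.1.10, Day 1 monitoring, extended observation, the Day 2 repeat after drug-treated bradycardia, written return instructions and a round-the-clock contact line all apply regardless of footnote a. Section 12.2.6 allows more frequent assessments if clinically indicated. Appendix 3 reports that in multiple sclerosis trials the greatest mean fall in heart rate on Day 1 was 1.2 bpm, and that no rate below 40 bpm was observed.

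A reader might also infer more than the documents support:

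- **That the SAP confirms Day 1 and Day 5 as trigger days.** SAP 11.5 lists changes "at each of the available Baseline, Study Day 5, and Study Day 8 visits". Those are days on which monitoring is performed. Footnote a has the same performance days, so this does not separate the readings.
- **That 12.1.10 definitely requires a Day 5 repeat after a resolved, symptom-free QTcF prolongation.** It ties QTcF explicitly only to extended monitoring. The rest is inference.
- **That footnote a can never take effect.** A patient may report symptoms on Day 4 or Day 7. The point is only that nothing is scheduled then.
- **That adolescents are left without adequate monitoring.** Much of the adolescent text is redacted, so this cannot be judged.

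**Conclusion.** The point holds as a wording inconsistency in a safety procedure that should be corrected. Footnote a, read literally, uses reference days 3 days later (Day 5 step) and 2 days later (Day 8 step) than the natural reading of the other four statements, and neither of its days has a scheduled assessment. A site relying on Table 2 alone could omit the repeat at a dose increase after an earlier issue had resolved.

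The reach is small. Appendix 3 reports admission to both adult cohorts in the past tense, so the change mainly concerns patients still to be dosed, such as adolescents. The documents give no frequency for such findings, so the number of patients affected cannot be estimated. The SAP 11.5 summaries of Day 1, 5 and 8 monitoring are descriptive, and nothing here bears on an efficacy analysis, the sample size or an error rate.

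The conclusion rests on two assumptions: that the previous day of dose escalation means the previous day on which the dose was started or raised, and that some Day 1 or Day 5 findings resolve before the next step and still count as cardiac issues.

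**What to change.** Reword the condition in footnote a so that the Day 1 assessments are repeated:

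> on Day 5 if cardiac issues were identified on Day 1, and on Day 8 if cardiac issues were identified on Day 5 (see Section 12.1.10)

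Name the same days in 12.1.4 and 12.1.10 and issue a site clarification. SAP 11.5 and 11.8 restate the rule as background; align their wording at the next revision, with no change to the analyses.

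The cost is one footnote, one sentence in each of two protocol sections, and the clarification. No scheduled visit or procedure is added. Extending the trigger to issues noticed on any day between the steps is an option for the sponsor. It would be a wider safety rule and could add monitoring sessions, and it is not needed to remove the inconsistency.

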7.3. Trial Periods

It is recommended that the trial visits are scheduled in the morning. On days of trial visits when trough PK samples are to be drawn, patients should be instructed to withhold the dose until the office visit, and the dose will be administered during the visit. At the Induction 2 (Week 5) visit, PK evaluations will be 2 to 6 hours after dosing. Therefore, patients should be instructed to take investigational drug at home prior to arriving for this visit.

Whenever possible, the sequence of assessments should remain constant and at approximately the same time of day throughout the trial.

It is recommended that procedures are performed in the following order (note that not all procedures are performed at every visit):

- Spontaneous or solicited AE reporting
- ECG
- Vital signs
- Clinical laboratory tests, including predose PK sampling
- Physical examination
- Efficacy assessments
- Investigational drug administration (on visits when trough PK blood draws are collected)

7.3.1. Screening Period

Written, signed, and dated informed consent/assent from the patient or patient's parent/legal guardian prior to the performance of any trial-related procedures must be obtained by the Investigator or designee (refer to [Section 16.3](#) for further details regarding obtaining patients informed consent/assent). A copy of the signed informed consent form (ICF)/assent must be given to the patient for his/her records.

Screening procedures must be completed within 35 days prior to receiving the first dose of investigational drug. All Screening assessments and procedures as per [Table 1](#) (IP and MP) are to be performed by the Investigator or a qualified designee.

A screen failure is defined as a patient or patient's parent/legal guardian who has given informed consent/assent, and failed to meet the inclusion and/or exclusion criteria. Patients who fail to meet the inclusion/exclusion criteria can be rescreened per Investigator discretion. Additional screening attempts beyond the first should be approved by the Medical Monitor prior to rescreening. Each patient or patient's parent/legal guardian must be re-consented/re-assented prior to each screening attempt.

During Screening the patient's prior use of medications to treat UC and whether they responded to adequate treatment with each medication will be assessed and documented. When considering response, an adequate treatment regimen for each of the following medications will be defined as:

- Oral aminosalicylates ≥ 2.4 g/day for at least 8 weeks
- Corticosteroids: oral prednisone ≥ 30 mg or budesonide MMX ≥ 9 mg for at least 2 weeks or intravenous corticosteroids for 1 week
- Immunomodulators: oral azathioprine ≥ 1.5 mg/kg or 6-mercaptopurine ≥ 0.75 mg/kg or methotrexate ≥ 12.5 mg/week for at least 8 weeks
- TNF- α antagonist (approved for marketing at an approved labeled dose) used for induction therapy for at least 4 weeks or recurrence of disease activity despite scheduled maintenance therapy

It will also be documented when the patient has been intolerant to one of these therapies (eg, unable to achieve doses, dose levels, or treatment durations because of treatment-related side effects and/or laboratory abnormalities).

The endoscopy at Screening must confirm disease extent, defined as 1) left-sided colitis (up to the splenic flexure), or 2) extensive colitis (beyond the splenic flexure).

If a colonoscopy is required at Screening, it should include removal of any adenomatous polyps prior to trial entry and documented evidence of surveillance for dysplasia for all patients with left-sided colitis of > 12 years duration and total or extensive colitis of > 8 years duration.

7.3.2. Induction and Maintenance Periods

Eligible patients will be randomized to treatment on Day 1 of both the Induction and Maintenance Periods. Visits, assessments, and procedures will be performed as per the Schedule of Events in [Table 1](#). Guidelines for dose escalation are in [Section 7.1](#).

7.3.3. Early Termination

For patients who discontinue the trial for any reason, every attempt should be made to complete the assessments detailed in the End of Treatment/Early Termination visit and the 30-day and 90-day Safety Follow-up Visits in the Schedule of Events ([Table 1](#)).

[REDACTED]

7.3.5. Relapse Assessment Visit

If during the MP the Investigator becomes aware of a potential relapse outside the normal visit schedule, patients should be evaluated for relapse as outlined in the Schedule of Events (Table 1).

7.3.6. Safety Follow-Up

For patients who discontinue the trial for any reason, every attempt should be made to return to the study site in order to complete the assessments detailed in the 30-day and 90-day Safety Follow-up Visits in the Schedule of Events (Table 1).

PK and hematology samples will be collected in all patients at the 30-day and 90-day visit. For patients with a confirmed ALC below the 200 cells/ μ L limit at the 30-day or 90-day Safety Follow Up Visit, central laboratory testing will continue every 14 days (\pm 3 days) after these visits until the ALC is above the lower limit of normal. In addition, additional safety assessments may be required for patients who have an ongoing AE or safety issue at the 90-day Safety Follow-up Visit, at the Investigator's discretion. Patients may be followed as necessary for an additional period of time after the 90-day Safety Follow-up Visit to review the results of any assessments which were conducted at the 90-day Safety Follow-up Visit.

7.3.7. Study Stopping Rules

The Sponsor has the right to terminate the trial for safety reasons. In addition, the Sponsor may terminate the trial for administrative reasons. In all cases, all necessary measures have to be taken to guarantee appropriate safety follow-up of all patients already included in the trial.

The Institutional Review Board (IRB) or Independent Ethics Committee (IEC) and the Regulatory Authorities will be informed in writing about any termination of the trial.

